11.2.1 Adverse Events of Special Interest

AEs of special interest include pulmonary hemorrhage, gastrointestinal bleeding, and hypersensitivity reactions. The list of PTs used to search for AEs of special interest is provided in [Appendix I](#) and was reviewed by Jazz Drug Safety & Pharmacovigilance and an independent DMC.

The following summaries will be provided:

- Summary of TEAEs of special interest: Pulmonary hemorrhage

- Summary of TEAEs of special interest: Pulmonary hemorrhage by age group
- Summary of TEAEs of special interest: Gastrointestinal bleeding
- Summary of TEAEs of special interest: Gastrointestinal bleeding by age group
- Summary of TEAEs of special interest: Gastrointestinal bleeding likely pre-existing neurological or neonatal conditions
- Summary of TEAEs of special interest: Gastrointestinal bleeding likely pre-existing neurological or neonatal conditions by age group
- Summary of TEAEs of special interest: Hypersensitivity reactions
- Summary of TEAEs of special interest: Hypersensitivity reactions by age group

The following listings will be provided:

- Listing of AEs of special interest: Pulmonary hemorrhage
- Listing of AEs of special interest: Gastrointestinal bleeding
- Listing of AEs of special interest: Gastrointestinal bleeding likely pre-existing neurological or neonatal conditions
- Listing of AEs of special interest: Hypersensitivity reactions

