The safety of defibrotide 25 mg/kg/day as prophylaxis has been demonstrated in children undergoing myeloablative conditioning considered to be at high risk of developing VOD (Corbacioglu et al. 2012). Incidences of AEs, serious adverse events (SAEs), and events leading to discontinuation were similar between the defibrotide and control groups (207 SAEs in 108 patients in the defibrotide group and 231 SAEs in 103 patients in the control group). Although the most common AE considered by the investigator to be related to defibrotide was hemorrhage, the cumulative incidence of hemorrhage was similar between groups (39 [22%] of 177 patients in the defibrotide group vs 37 [21%] of 176 patients in the control group;  $p=0.8176$ ). Overall, most fatal AEs were either neoplasms (12 [7%] of 177 patients in the defibrotide group and 14 [8%] of 176 patients in the control group) or infections (6 [3%] patients in the defibrotide group and 11 [6%] patients in the control group). In the intent-to-treat (ITT) population, patients who underwent allogeneic HSCT and who received defibrotide prophylaxis had a lower overall incidence of acute graft-versus-host disease (GvHD) (all grades) by Day +30 and +100 post-HSCT compared with those in the control group (Day +30 post-HSCT, 34% vs 53%  $p=0.004$ ; Day +100 post-HSCT, 47% vs 67%  $p=0.002$ ). A lower incidence of acute GvHD was also observed when grade 1 toxicity was excluded.

Defibrotide (JZP-381)  
Clinical Trial Protocol: 15-007 Version 4.0

Jazz Pharmaceuticals, Inc.  
20 August 2018

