## 1.6 Potential Risks

Potential risks associated with defibrotide administration include the risk of bleeding in patients with VOD after HSCT, hypersensitivity reactions, and risk to pregnancy.

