## 4.2 Exclusion Criteria

Patients who meet any of the following criteria will be excluded from the study. Study treatment is defined as defibrotide prophylaxis in addition to BSC or BSC alone.

1. Patient has hemodynamic instability within 24 hours before the start of study treatment.
2. Patient has acute bleeding that is clinically significant within 24 hours before the start of study treatment, defined as either of the following (a or b):
  - a. hemorrhage requiring >15 cc/kg of packed red blood cells (e.g., pediatric patient weighing 20 kg and requiring 300 cc packed red blood cells/24 hours, or an adult weighing >70 kg and requiring 3 units of packed red blood cells/24 hours) to replace blood loss, or
  - b. bleeding from a site which, in the investigator's opinion, constitutes a potential life-threatening source (e.g., pulmonary hemorrhage or central nervous system bleeding), irrespective of amount of blood loss
3. Patient used any medication that increases the risk of bleeding within 24 hours before the start of study treatment, including, but not limited to, systemic heparin, low molecular weight heparin, heparin analogs, alteplase (tPA), streptokinase, urokinase, antithrombin III (ATIII), and oral anticoagulants including warfarin, and other agents that increase the risk of bleeding. Patients may receive heparin or other anticoagulants for routine central venous line management and intermittent dialysis or ultrafiltration. Fibrinolytic instillation for central venous line occlusion is also permitted.  
Note: Heparin use will be allowed in both treatment arms (up to a maximum of 100 U/kg/day).
4. Patient is using or plans to use an investigational agent for the prevention or treatment of VOD.
5. Patient, in the opinion of the investigator, may not be able to comply with the safety monitoring requirements of the study.
6. Patient or parent/legal guardian or representative has a psychiatric illness that would prevent the patient or parent/legal guardian or representative from giving informed consent and/or assent.
7. Patient has a serious active disease or co-morbid medical condition, as judged by the investigator, which would interfere with the conduct of this study.

Defibrotide (JZP-381)  
Clinical Trial Protocol: 15-007 Version 4.0

Jazz Pharmaceuticals, Inc.  
20 August 2018

8. Patient is pregnant or lactating and does not agree to stop breastfeeding.
9. Patient has a known history of hypersensitivity to defibrotide or any of the excipients.

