20.3 PTs for Gastrointestinal Bleeding likely pre-existing neurological or neonatal conditions

Anal haemorrhage
Anal ulcer haemorrhage
Anastomotic haemorrhage
Anastomotic ulcer haemorrhage
Anorectal varices haemorrhage
Diverticulitis intestinal haemorrhagic
Diverticulum intestinal haemorrhagic
Duodenal operation
Duodenal vascular ectasia
Gastric antral vascular ectasia
Gastric haemangioma
Gastric varices haemorrhage
Gastritis alcoholic haemorrhagic
Gastrointestinal anastomotic leak
Gastrointestinal angiectasia
Gastrointestinal angiodysplasia haemorrhagic
Gastrointestinal polyp haemorrhage
Haemorrhoidal haemorrhage
Mallory-Weiss syndrome
Melaena neonatal
Neonatal gastrointestinal haemorrhage
Oesophageal varices haemorrhage
White nipple sign

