Eosinophilic granulomatosis with polyangiitis
Epidermal necrosis
Epidermolysis
Epidermolysis bullosa
Epiglottic oedema
Erythema multiforme
Erythema nodosum
Exfoliative rash
Eye allergy
Eye oedema
Eye swelling
Eyelid oedema
Face oedema
Fixed drug eruption
Giant papillary conjunctivitis
Gingival oedema
Gingival swelling
Gleich's syndrome
Haemorrhagic urticaria
Hand dermatitis
Henoch-Schonlein purpura
Henoch-Schonlein purpura nephritis
Heparin-induced thrombocytopenia
Hereditary angioedema
Hypersensitivity

Hypersensitivity vasculitis
Idiopathic urticaria
Immediate post-injection reaction
Immune thrombocytopenic purpura
Immune tolerance induction
Immune-mediated adverse reaction
Implant site dermatitis
Implant site hypersensitivity
Implant site rash
Implant site urticaria
Incision site dermatitis
Incision site rash
Infusion site dermatitis
Infusion site eczema
Infusion site hypersensitivity
Infusion site rash
Infusion site recall reaction
Infusion site urticaria
Infusion site vasculitis
Injection site dermatitis
Injection site eczema
Injection site hypersensitivity
Injection site rash
Injection site recall reaction
Injection site urticaria
Injection site vasculitis
Instillation site hypersensitivity
Instillation site rash
Instillation site urticaria
Interstitial granulomatous dermatitis
Intestinal angioedema
Iodine allergy
Kaposi's varicelliform eruption
Kounis syndrome
Laryngeal oedema
Laryngitis allergic
Laryngospasm
Laryngotracheal oedema
Limbal swelling
Lip oedema
Lip swelling
Mast cell degranulation present
Medical device site dermatitis

Medical device site eczema
Medical device site hypersensitivity
Medical device site rash
Medical device site recall reaction
Medical device site urticaria
Mouth swelling
Mucocutaneous rash
Multiple allergies
Nephritis allergic
Nikolsky's sign
Nodular rash
Oculomucocutaneous syndrome
Oculorespiratory syndrome
Oedema mouth
Oral allergy syndrome
Oropharyngeal blistering
Oropharyngeal spasm
Oropharyngeal swelling
Palatal oedema
Palatal swelling
Palisaded neutrophilic granulomatous dermatitis
Palpable purpura
Pathergy reaction
Periorbital oedema
Pharyngeal oedema
Pruritus allergic
Radioallergosorbent test positive
Rash
Rash erythematous
Rash follicular
Rash generalised
Rash macular
Rash maculo-papular
Rash maculovesicular
Rash morbilliform
Rash neonatal
Rash papulosquamous
Rash pruritic
Rash pustular
Rash rubelliform
Rash scarlatiniform
Rash vesicular
Reaction to azo-dyes

Reaction to colouring
Reaction to drug excipients

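### The special-interest bleeding lists leave out CNS and urinary bleeding, plan no count of subjects with any bleed, put nosebleeds in the pulmonary total, and report some GI bleeds under a heading that does not fit them

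*SAP*

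**What the plan says.** Protocol Section 1.6 opens with "Potential risks associated with defibrotide administration include the risk of bleeding in patients with VOD after HSCT, hypersensitivity reactions, and risk to pregnancy". Section 1.6.1 discusses hemorrhage without restricting it to a site. In describing the earlier pediatric prophylaxis trial, Section 1.3 says that "the most common AE considered by the investigator to be related to defibrotide was hemorrhage" and gives a subject-level incidence over all hemorrhage: "39 [22%] of 177 patients in the defibrotide group vs 37 [21%] of 176 patients in the control group". Exclusion criterion 2b in Section 4.2 illustrates a life-threatening bleeding source with "pulmonary hemorrhage or central nervous system bleeding".

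SAP Section 11.2.1 defines three AESI topics: "AEs of special interest include pulmonary hemorrhage, gastrointestinal bleeding, and hypersensitivity reactions". Appendix I lists the terms: 20.1 for pulmonary hemorrhage (which includes epistaxis), 20.2 for GI bleeding, 20.3 under the heading "PTs for Gastrointestinal Bleeding likely pre-existing neurological or neonatal conditions", and 20.4 for hypersensitivity. List 20.3 has its own summary, by-age summary and listing. SAP Section 5 notes that these AESIs are an addition to the protocol.

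**The concern.** For a drug whose leading safety question is bleeding, a reader will want to know how many subjects bled in each arm, and how many bled at the sites the protocol treats as life-threatening. The AESI tables answer this for the lung and the gut only.

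Within those two sites the groupings are also hard to interpret. A pulmonary total that mixes nosebleeds with alveolar hemorrhage does not measure serious lung bleeding. A main GI table from which some gut bleeds have been moved elsewhere does not measure GI bleeding. At stake are the headline bleeding comparisons in the study report, not the efficacy result.

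**Working it through.** **1. The earlier trial's figure.** Inputs are from Protocol Section 1.3. 39/177 = 22.0% and 37/176 = 21.0%, a difference of 1.0 point. A Pearson chi-square without continuity correction gives p = 0.817, against the stated 0.8176 (the test is not named). The figure reproduces. It counts subjects with any hemorrhage, which is the type of number at issue here.

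**2. Whether the planned tables yield such a number.** SAP Section 11.2 counts a subject once per preferred term and once per system organ class. No row counts a subject once across all bleeding. The AESI tables cannot be added to obtain it. If the lung and GI tables show proportions L and G in an arm, the proportion with either lies between max(L, G) and L + G, and bleeds at other sites are still missing. The documents give no site-specific rates, so this cannot be narrowed.

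**3. What the lists contain.** Counts are from SAP Appendix I:

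| List | Terms | CNS or urinary | Variceal | Anorectal |
|---|---|---|---|---|
| 20.1 Pulmonary | 10 | 0 | 1 (bronchial) | 0 |
| 20.2 GI | 39 | 0 | 1 (intestinal) | 3 (rectal, rectal ulcer, haemorrhagic proctitis) |
| 20.3 Second GI list | 23 | 0 | 3 (oesophageal, gastric, anorectal) | 4 (anal, anal ulcer, anorectal varices, haemorrhoidal) |
| Total | 72 | 0 | 5 | 7 |

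Anorectal varices appears in both of the last two columns. List 20.3 therefore holds 3 of 5 variceal terms and 4 of 7 anorectal terms, while closely similar terms stay in 20.2. It also holds Mallory-Weiss syndrome.

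**4. Heading of 20.3 against its contents.** Of its 23 terms, none is neurological and two are neonatal (neonatal melaena and neonatal GI haemorrhage). The rule is not applied evenly either, because a neonatal respiratory tract haemorrhage term stays in main list 20.1. The summaries count treatment-emergent events, which SAP Section 11.2 defines as starting, or worsening, after the first study treatment. A bleed that was simply present before treatment would not be counted at all.

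**5. Effect on the main GI rate.** Suppose an arm of N subjects has m in the main GI table and k in the 20.3 table. The combined rate lies between max(m, k)/N and (m + k)/N. The main table is therefore low by at most k/N, and by nothing only if every subject in the 20.3 table also has a term from 20.2. Neither m nor k can be forecast from the documents.

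**6. Effect on the pulmonary rate.** Epistaxis is 1 of 10 terms, but its weight depends on how often it is reported, and the documents do not say. Every subject whose only listed event is a nosebleed raises the pulmonary hemorrhage rate.

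**The case against.** The best case for the plan is that nothing is lost. A CNS bleed would appear by arm in the general treatment-emergent table by organ class and term. Where applicable, it would also appear in the serious, treatment-related, Grade 3 or 4, discontinuation and fatal summaries, and in the listings. List 20.3 is reported in full next to the main GI table. The AESIs go beyond what the protocol asked for, and the sponsor's safety group and an independent DMC reviewed the lists. The heading of 20.3 may mean that the lesion, such as a varix, existed before treatment, not the bleed.

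Much of this stands. It shows that the data are available. It does not supply a count of subjects with any bleed. Nor does it explain why intestinal varices are in one list and oesophageal varices in another. A new bleed from an existing lesion is still treatment-emergent.

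A reader might go further in four ways that the documents do not support.
- **All bleeding outside lung and gut is missing.** Intra-abdominal haematoma and mesenteric haemorrhage are in 20.2, and anastomotic haemorrhage is in 20.3.
- **Variceal and anorectal bleeds are dropped.** Only some are moved, and those are still tabulated as AESIs.
- **Comparison with the earlier trial becomes impossible.** All events are coded and listed, so a count could be made later. The documents do not say how that trial defined hemorrhage, so an exact match cannot be promised in any case.
- **The hypersensitivity list is full of GvHD rash and could make defibrotide look protective.** The list does include "Rash maculo-papular" and other non-specific terms, but no GvHD term. Protocol Section 6.8.1.1 asks for the diagnosis, not its signs, as the recorded event. The lower GvHD rate in the earlier trial (34% vs 53% by Day +30) covers allogeneic patients under 18 and all grades of acute GvHD, not skin disease alone. Nothing in the documents says how often a GvHD rash would be coded as rash, so no size can be attached to this.

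**Conclusion.** The concern holds as a defect in how bleeding is grouped and summarised. SAP Section 11.2.1 and Appendix I give no CNS or urinary bleeding term in 72, no subject-level any-hemorrhage count, a pulmonary total that includes epistaxis, and a main GI total that omits some treatment-emergent GI bleeds.

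The term counts are exact. The effect on reported rates is not quantifiable beforehand. It rests on the assumption that at least some subjects have bleeds outside the lung and gut, nosebleeds only, or GI bleeds found only in list 20.3. Type I error, power and the primary endpoint are unaffected.

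The breadth of the hypersensitivity list is a lesser matter. Non-specific rash, dermatitis and shock terms could bring in events from other causes, which justifies a supportive summary but not a claim of bias in either direction.

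**What to change.** In SAP Section 11.2.1 and Appendix I, before database freeze:

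- Add an any-hemorrhage group that counts each subject once, by arm and study phase. Give CNS hemorrhage its own row, and show Grade 3 or higher and fatal counts.
- Merge list 20.3 into the GI bleeding list and show it only as a footnoted subset. In doing so, check the few entries that do not in themselves denote bleeding, such as duodenal operation and GI anastomotic leak.
- Take epistaxis out of the pulmonary list and report it separately.
- Optionally, add a supportive hypersensitivity summary without the non-specific rash, dermatitis and shock terms, and keep the present list as it is.

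All of this uses adverse event data that will already be coded. The cost is an appendix revision and a few more tables, with a higher reported bleeding count that should be explained in the report.

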11.3 Laboratory Assessments

For all hematology, coagulation, and chemistry parameters, the lab values at baseline and each of the postbaseline assessments will be summarized and presented using descriptive statistics. See Section [8.4.1](#) for the identification of the assessments used in the analyses. For each of the postbaseline assessments, change between baseline and that assessment in a specific lab value will be calculated as follows,

Change from baseline = [Lab value at the post-baseline assessment] – [Lab value at baseline],

and will be summarized and presented using descriptive statistics. If the lab value is missing at either baseline or a specific post-baseline assessment for a subject, change from baseline will be missing.

- Summary of clinical laboratory results: Hematology
- Summary of clinical laboratory results: Chemistry
- Summary of clinical laboratory results: Coagulation

For each of the following select laboratory parameters: total bilirubin, serum creatinine, absolute neutrophil count, and platelet count, a shift table from baseline grade to the highest postbaseline grade will be provided:

- Shift table of selected postbaseline laboratory results from baseline

All laboratory results will be listed. In addition, a listing of subjects who have abnormal postbaseline lab values for select lab parameters (total bilirubin, serum creatinine, absolute neutrophil count, and platelet count) will be provided with corresponding normal ranges. The following listings will be provided:

- Listing of clinical laboratory results: Hematology
- Listing of clinical laboratory results: Chemistry
- Listing of clinical laboratory results: Coagulation

- Listing of subjects with abnormal post-baseline laboratory values

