### 2.2 Secondary Objectives

The key secondary objective of the study is to compare the efficacy of defibrotide prophylaxis in addition to BSC (DP arm) vs BSC alone (BSC arm) for the prevention of VOD as measured by VOD-free survival by Day +100 post-HSCT in patients who are at high risk or very high risk for developing VOD.

Other secondary objectives of the study are as follows:

- To further compare the efficacy of defibrotide prophylaxis in addition to BSC (DP arm) vs BSC alone (BSC arm) on additional variables, as follows:
  - Incidence of VOD by Day +30 post-HSCT
  - VOD-free survival by Day +180 post-HSCT
  - Non-relapse mortality (NRM) by Day +100 and by Day +180 post-HSCT
  - Incidence of VOD-associated multi-organ dysfunction (MOD) (i.e., severe VOD) by Day +30 and by Day +100 post-HSCT (in those patients who develop VOD)
  - Proportion of patients who have resolution of VOD by Day +180 post-HSCT and time to resolution of VOD (in those patients who develop VOD)
  - Incidence of VOD after Day +30 post-HSCT, by Day +100, and by Day +180 post-HSCT
- To compare the health-related quality of life using the following questionnaires:
  - 5-Level EuroQol-5D (EQ-5D-5L) (adults only)
  - EuroQol-5D for Youth (EQ-5D-Y), proxy version 1 (pediatric patients 4 to 7 years of age)
  - EQ-5D-Y, self-report version 1 (pediatric patients 8 to <16 years of age)
- To characterize the pharmacokinetics of defibrotide
- To compare the overall safety of defibrotide in addition to BSC vs BSC alone, including AE profile, SAE profile, laboratory abnormalities, and vital signs (including peri-infusional vital signs for patients who receive defibrotide)
- To compare the overall safety of defibrotide in addition to BSC vs BSC alone by comparing the incidence of grades 2, 3, and 4 acute GvHD by Day +30, Day +100, and Day +180 post-HSCT, and the incidence of chronic GvHD at Day +180 post-HSCT
- To compare graft failure and time to neutrophil and platelet engraftment

Defibrotide (JZP-381)  
Clinical Trial Protocol: 15-007 Version 4.0

Jazz Pharmaceuticals, Inc.  
20 August 2018

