#### **9.14.2 Clinical Laboratory Results**

Laboratory parameters will be summarized (e.g., total bilirubin, serum creatinine). Descriptive statistics (n, mean, standard deviation, median, minimum, and maximum) as well as changes from baseline (i.e., within 24 hours before conditioning begins for the DP arm and on the day conditioning begins for the BSC arm) will be summarized by study phase and treatment received during the Prophylaxis Phase. The number and percentage of patients with abnormal values postbaseline and other summary statistics (i.e., mean, minimum, maximum, standard deviation, and number of patients) will be presented by study phase and treatment received during the Prophylaxis Phase for each laboratory parameter as per protocol schedule.

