3 PURPOSE

This Statistical Analysis Plan (SAP) provides a detailed and complete description of the planned statistical analyses for the final analysis of Study 15-007 to support the Clinical Study Report (CSR). Mock tables, listings, and figures shells will be provided in a separate supporting document.

This SAP complies with the International Council for Harmonisation (ICH) Harmonised Tripartite Guideline Topic E9, Statistical Principles for Clinical Trials. The current version is based on Protocol version 4.0 dated 20 August 2018.

Biomarker and immunogenicity analysis plans and results will be provided in separate documents.

All decisions regarding the final analysis of the study results, as defined in this SAP document, will be made prior to database freeze of the study data.

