4.3.2.3 Other Secondary Endpoints

Other secondary efficacy endpoints will be tested without multiplicity adjustments, and nominal p-values will be reported. Other secondary efficacy endpoints include the following:

- Incidence of VOD by Day +30 post-HSCT
- VOD-free survival by Day +180 post-HSCT
- NRM by Days +100 and +180 post-HSCT

- Incidence of VOD-associated MOD (ie, severe VOD) by Days +30 and +100 post-HSCT (in those subjects who develop VOD)
- Proportion of subjects who have resolution of VOD by Day +180 post-HSCT and time to resolution of VOD
- Incidence of VOD after Day +30 post-HSCT up to Days +100 and +180 post-HSCT
- Health-related quality of life using EQ-5D-5L (adults only), EQ-5D-Y (proxy version 1; pediatric subjects 4 to 7 years of age), and EQ-5D-Y (self-report version 1; pediatric subjects 8 to <16 years of age)
- Pharmacokinetics of defibrotide
- Safety of defibrotide in addition to BSC vs BSC alone, including AE profile, SAE profile, laboratory abnormalities, and vital signs
- Incidence of Grades 2, 3, and 4 acute GvHD by Days +30, +100, and +180 post-HSCT, and the incidence of chronic GvHD by Day +180 post-HSCT
- Graft failure and time to neutrophil and platelet engraftment

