5 CHANGES IN THE CONDUCT OF PLANNED ANALYSES

Three TEAEs of special interest (pulmonary hemorrhage, gastrointestinal bleeding, and hypersensitivity reactions) will be summarized. This is not specified in the protocol.

Section 10.1 clarifies censoring rules for subjects who don't undergo HSCT. The protocol defines the timing variable for these subjects but does not describe how these subjects who are not at risk of post-HSCT events should be censored.

Section 10.1 also added censoring rules for subjects who develop VOD prior to HSCT. This scenario is a possible outcome, albeit rare, and was not addressed in the protocol.

Section 8.2.1 clarifies how baseline is defined. The protocol defines baseline as follows: "Baseline/Study Day 1 is defined as the day before conditioning begins for patients randomized to the DP arm and the day that conditioning begins for patients randomized to the BSC arm." As the first dose of defibrotide is administered within 24 hours prior to the first dose of conditioning for subjects randomized to DP arm, the two definitions should result into the same Study Day 1 if the subjects strictly follow the protocol. In practice, it is possible that the subjects receive the first dose of defibrotide and then do not start conditioning on the next day. Thus, the definition in the protocol could result in a baseline assessment that occurs after defibrotide administration begins. For safety analyses, the baseline value should be the last assessment taken prior to study drug administration. For this reason, the definitions of Baseline/ Study Day 1 and of baseline values were further clarified in the SAP and this is the default definition used in the analyses.

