7 GENERAL CONSIDERATIONS

7.1 General Methods

The statistical principles applied in the design and planned analyses of this study are consistent with ICH E9 guidelines (ICH 1998).

Analysis datasets will be created according to Clinical Data Interchange Standards Consortium (CDISC) standards. SAS® version 9.3 (or higher) will be used to perform all data analyses and to generate tables, figures, and listings.

Summaries will order the treatment display from left to right as follows: DP (study treatment), BSC (control), and Total if a total column if applicable. Listings will include the randomized treatment arm, unique subject number, age, gender, and race. They will be sorted by treatment arm and then by subject number within treatment arm.

Unless otherwise specified, continuous data will be summarized using descriptive statistics comprising the number of subjects with data to be summarized (n), mean, standard deviation (SD), median, minimum (min) and maximum (max). Categorical variables will be presented using counts and percentages. Every category will be kept in the summary even if it has 0 subjects. Summary statistics of central tendency will be reported to one more decimal place than the collected data. Summary statistics of variability will be reported to one more decimal place than the commensurate measure of central tendency. For example, the mean and median for age will be reported to one decimal place because it is collected in full years. The standard deviation

of age will then be reported to 2 decimal places. P-values > 0.9999 will be presented as ' >0.9999 ' and p-value < 0.0001 will be presented as ' < 0.0001 '.

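### SAP 11.3 plans abnormality output for four laboratory parameters, where protocol 9.14.2 promises the number and percentage of patients with abnormal values for each one, and SAP section 5 does not declare the reduction

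*SAP*

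**What the plan says.** Protocol 9.14.2 has two layers. Laboratory values and changes from baseline are to be summarized descriptively. In addition, "The number and percentage of patients with abnormal values postbaseline and other summary statistics" are to be shown by study phase and "treatment received during the Prophylaxis Phase for each laboratory parameter as per protocol schedule". The objective behind this is in protocol 2.2, which compares overall safety between the arms "including AE profile, SAE profile, laboratory abnormalities, and vital signs". SAP 4.3.2.3 repeats it as a secondary endpoint: "Safety of defibrotide in addition to BSC vs BSC alone, including AE profile, SAE profile, laboratory abnormalities, and vital signs".

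SAP 11.3 keeps the first layer for all hematology, coagulation and chemistry parameters. Under SAP 7.1, "continuous data will be summarized using descriptive statistics comprising the number of subjects with data to be summarized (n), mean, standard deviation (SD), median", with the smallest and largest values. The second layer is cut back. The only abnormality outputs are a shift table ("For each of the following select laboratory parameters: total bilirubin, serum creatinine, absolute neutrophil count, and platelet count, a shift table from baseline grade", ending at the highest postbaseline grade) and a listing of subjects with abnormal postbaseline values, both confined to those four parameters. All laboratory results are also listed.

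SAP section 5 sets out changes from the protocol. It opens with an addition: "Three TEAEs of special interest (pulmonary hemorrhage, gastrointestinal bleeding, and hypersensitivity reactions) will be summarized. This is not specified in the protocol". It then covers censoring without transplant, VOD before transplant, and the definition of baseline. Neither section 5 nor the SAP modification history mentions laboratory abnormality summaries.

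**The concern.** A count promised for every parameter in the protocol appears in the SAP, in a different form, for four parameters only and without a declared change. Someone programming from the SAP would produce no by-arm abnormality rate for coagulation, transaminases, hemoglobin or electrolytes.

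What is at stake is part of the safety comparison. Hemorrhage is a named risk of defibrotide (protocol 1.6.1), and protocol 1.2 describes the drug as having no significant systemic anticoagulant effect. Rates of abnormal aPTT and INR by arm bear directly on that description. Clinically significant laboratory changes do reach the adverse event tables (protocol 6.8.2.1), but only after an investigator has judged them significant, and in this open-label trial the investigator knows the arm. For most parameters the SAP commits to no abnormality rate that is free of that judgement.

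**Working it through.** The point rests on setting the texts side by side and counting. There is no planned figure to reproduce.

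1. **Lines in scope (protocol Table 7).** Serum chemistry has 18 lines, of which cystatin C and GFR are optional: 18 − 2 = 16. Hematology has 5 and coagulation has 2. Required lines: 16 + 5 + 2 = 23.

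2. **Lines with abnormality output (SAP 11.3).** Bilirubin, creatinine, platelets, and white cell count with differential (through the absolute neutrophil count): 4.

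3. **Lines without it.** 23 − 4 = 19, or 19/23 = 83%. If calculated creatinine clearance (derived from creatinine) and hematocrit (paired with hemoglobin) are set aside as near-duplicates, the count is 21 − 4 = 17 of 21. Both coagulation lines are uncovered on either count.

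4. **Whether the descriptive tables could stand in.** SAP 8.4 selects one assessment per analysis window, or averages those on the selected date, so other values in the window are not tabulated. SAP Table 1 indexes days as assessment date − transplant date + 1, and its first postbaseline window starts at 1, the day of transplant. Values drawn during conditioning have an index of 0 or less and enter no visit row. The windows end at 66, resume at 96, end at 106 and resume at 171, so values at 67–95 and 107–170 also enter no prophylaxis-phase visit row. Means, medians and extremes of selected values do not give the number of patients who were ever abnormal.

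5. **Whether this is the SAP's general style.** Protocol 9.14.3 makes a parallel promise for vital signs. SAP 11.4 meets it with a low/normal/high classification and a shift table for all five vital signs. Among these two sets of measurements, only the laboratory promise was narrowed.

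6. **The four covered parameters.** Even here the SAP names a grade shift table and a listing, not a count and percentage abnormal. A shift table would normally yield such counts, so these four are treated as covered.

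**The case against.** The strongest reply is that little is lost in practice. Every parameter is summarized by arm and phase without investigator judgement, and every result is listed. Clinically significant changes are recorded as adverse events and tabulated by maximum grade. Bleeding, the clinical concern behind coagulation testing, has its own pulmonary and gastrointestinal special-interest tables (SAP 11.2.1), and transfusions are summarized by arm (SAP 12). Many parameters will be abnormal in most patients after transplant, so any-value-out-of-range rates may separate the arms poorly. All of this stands, and it is why the point is minor. It does not remove an undeclared conflict with a protocol commitment.

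The table shells are also out of view: "Mock tables, listings, and figures shells will be provided in a separate supporting document". They may contain the protocol's table. The claim is therefore only that the SAP text does not commit to it. A reader might infer that the table will not be produced, or that a coagulation signal is being kept out of sight. The documents support neither.

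A reader might also try to size the problem by the difference in observation time between arms, since rescue is expected more often in the BSC arm and ends the prophylaxis phase. That difference affects how the added table is read. It does not measure what is lost by reporting four parameters. Nor do the documents supply the inputs. The 14% and 28% planning rates are for VOD or death with VOD centrally adjudicated, whereas the phase ends at rescue, which follows investigator diagnosis and is optional. Without VOD the phase runs to study completion, not Day +30, and the timing of rescue is not given.

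**Conclusion.** The conflict is real and its severity is minor. As written, the SAP leaves 19 of 23 required laboratory lines without the abnormality count and percentage that protocol 9.14.2 promises, and section 5 does not declare this. The consequence is confined to descriptive safety reporting on a named secondary objective; the primary and key secondary analyses are untouched and no data are lost.

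Two conditions apply. The line count treats cystatin C and GFR as optional and the neutrophil count as covering the white cell line. The conclusion concerns the SAP text, not the unseen shells. It does not extend to a demand for more grade shift tables, because the protocol promises counts and percentages, not shifts.

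**What to change.** In SAP 11.3 add, by arm and study phase, the n (%) of subjects with any postbaseline value outside the local reference range, for each Table 7 parameter.

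- **Values used.** Use all postbaseline values, not only those selected by visit window. Protocol 9.14.2 does not say whether the count is per visit or over the phase; counting over the phase is a choice and should be stated.
- **Start of the count.** Use the SAP 8.2.2 baseline in both arms. In the DP arm this counts values drawn after the first defibrotide dose but before conditioning. Starting both arms at conditioning would look more even but would drop those on-drug values from a safety table.
- **Denominators.** Beside each rate, show the number of subjects with data and the number of samples or the observation time.
- **Footnote to the aPTT and INR rows.** Anticoagulants prohibited with defibrotide may be used in the BSC arm, and heparin up to 100 U/kg/day is allowed in both arms (protocol 5.7.6).

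If reporting on four parameters is intended, declare it in SAP section 5 with a reason instead.

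The cost is SAP wording and one descriptive table per phase, from data already collected; sites already supply reference ranges (protocol 6.8.2). The downsides are that rates will be high for many parameters after transplant, coagulation may be drawn only weekly (protocol 7.2.1.2), and observation differs by arm because the prophylaxis phase ends at rescue. The table should therefore be read as descriptive only.
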